participants' future goals and attitudes using the **Future Orientation Scale** (Steinberg et al., 2009), and the **Goal Orientation Scale** (Child Trends). **Counselor Measures** (Feldstein et al., 2012) to gather the counselor's subjective assessment of the MI and BAM interventions. We will administer the **Wechsler Abbreviated Scale of Intelligence** (WASI; Wechsler 1999) Vocabulary and Matrix Reasoning subtests and an fMRI **Theory of Mind** task (cartoon stories) (Sebastian et al., 2012) to evaluate basic cognitive skills. We will query youth's level of agreement with each presented counselor statement ([name] under review), presented in their individualized fMRI paradigm via likert scale immediately after their fMRI session in the **Scanner Exit Questionnaire**. We will assess client sleepiness during the scan with the Karolinska **Sleep Scale** (Akerstedt & Gillberg, 1990). Finally, we will administer the **Working Alliance Inventory** (Tracey & Kokotovic 1989) to all counselors and youth at the end of each session to assess youth and counselor perspectives of therapeutic alliance, along with the **Counselor and You** scale (Aron et al., 1992), client and counselor ratings of the **Most Important In-Session Clinical Moment** (Walsh 2004) and client and counselor ratings of the **Therapist's Level of Empathy and Warmth** (Miller & Moyers, 2013). Following Session 1, the counselor will select the 20 most relevant BAM or MI statements using the **BAM or MI Counselor Statement Selections** worksheet, which allows the NILE fMRI to be catered to individual participants.

Intervention Session 1:

Experimental Condition: Half of the enrolled youth will receive 2 60-minute MI sessions which explicitly target reducing problem drinking. All sessions will be conducted by a postdoctoral fellow or graduate-level counselor and will proceed according to our established adolescent MI manual ([name] et al 2008). The first session is focused on an open-ended exploration of youth's problem drinking behavior. This session is audio-recorded to facilitate the transfer of within-session statements to the fMRI task (see Session 1 MI).

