Control Condition: Half of the enrolled youth will be randomized to a control condition to help researchers isolate the mechanisms of MI that relate to behavior change. The control condition will receive 2 60-minute Brief Adolescent Mindfulness (BAM) sessions. The first session is focused on the normalization of the experience of intrusive thoughts, particularly worry and rumination; and an overview of mindfulness concepts including maintaining a nonjudgmental and present-focused mental state and engendering greater awareness of one's thoughts, feelings, reactions, environment and stressors.

Session 2 components.

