Intervention Session 2. Immediately after the scan, youth will meet with their study counselor in a private visit room within OHSU. The second MI session focuses on providing youth personalized feedback regarding their alcohol use (from their baseline data), working with youth to identifying high-risk drinking situations, and determining avenues to help reduce their problem drinking (see Session 2 MI). The BAM group receives mindfulness problem-solving strategies to practice in daily life and in addition, the counselor will discuss the connection between anxiety, stress, and worry with alcohol use, and will reiterate mindfulness concepts. The second intervention sessions for both groups will be audiotaped, but there will be no videotaping as the fMRI stimuli comes from Intervention Session 1 and thus verification is only required for the first session.

Follow-Up Procedures. Given that the impact of MI on youth distal behavior change (>6 month) is not well understood (Jensen et al 2011, Larimer & Cronce 2007), we will evaluate youth over a 12-month period using a near-identical behavioral measurement package administered at baseline (specifically, at 3-, 6-, and 12-months) to obtain an understanding of the nature and duration of brain-based factors in youths' alcohol treatment response. Certain questionnaires will only be administered at Session 1 because they capture a "past year" period (DPS, CTQ) or do not require readministration throughout the entire study (Arrest and Recidivism History, Family Substance Use). The PDS will only be administered at scan visits (Session 2 and the 3 month follow up). See Measures List for additional details. At each in-person visit, we will have the participant complete a breathalyzer and urinalysis to corroborate self-report of drug and alcohol use. For the 3-month follow up, in addition to the follow up procedures described above, participants will return to OHSU for a final MRI scan identical to the one completed in Session 2, and complete the **TLFB 3 Day Use Short Form** before scanning to check for recent substance use. Consistent with our prior NIH- and IRB-approved protocols, 6- and 12-month follow-ups can be completed in-person at a location convenient for youth (e.g., community centers; OHSU), but will be offered to participants as a combination phone (for the TLFB interview) and REDCap (for the remaining measures)

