questionnaire battery to eliminate the need for participants to travel to complete the visits. In cases where follow ups are conducted by phone/REDCap, no biological screening will occur (UA, breathalyzer, saliva). For participants who are unable to come to the OHSU campus for the 3-month follow up and corresponding MRI scan, phone/REDCap measures will be offered instead to minimize missing data.

Rationale for Choice of Intervention Approach and Study Duration.

We chose MI as the target behavioral alcohol treatment for this age group for several reasons. First, MI is recognized as an evidenced-based substance abuse treatment for youth (SAMHSA; <http://www.nrepp.samhsa.gov/>). At the same time, MI has also been identified as a treatment that warrants further investigation in the mechanisms of behavior change research (PAR-14-051). Second, important to this study, the theoretical mediators of MI are well-specified. MI seeks to promote behavior change through the use of specific therapist behaviors (e.g., MI-consistent statements) to elicit client speech in favor of change, constructs that can and have been objectively measured across both behavioral (Moyers & Martin 2006, Moyers et al 2007) and neuroimaging studies ([name] et al 2011b, [name] et al 2013b, [name] et al under review-c). Third, MI is one of the most widely-disseminated interventions, utilized across primary care through addictions treatment centers (Burke et al 2003, Jensen et al 2011). Thus, findings on brain based factors underlying MI response has a high potential for clinical and scientific impact ([name] & Chung 2013). Fourth, application of adult brain-based models to adolescents have not been supported; thus, evaluating youths' neurodevelopmentally-specific response to MI is critically important ([name] et al 2013b). And, we could find no published studies examining the impact of therapist behaviors on the adolescent brain. The unique contributions and ultimate effectiveness of MI cannot be evaluated without a comparison condition. For example, if the youth in the mindfulness condition show greater change in neurocircuitry related to cognitive control which corresponds to behavior change during follow up, as compared to the MI condition, then we know more about what components of the different interventions may or may not be having a positive impact on participants.

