The Impact of Attrition. In our prior NIAAA R01 with drinking youth (PI [name]), we have an established track-record of retaining ~84% of adolescents at our most distal (12 month) follow-up. Thus, we project losing 16% of the proposed sample, thus requiring **N = 243** youth to account for attrition.

Analysis Plan.

Analyses will be conducted to evaluate (1) the relationship between therapist behavior and youth brain response (BOLD), (2) the relationship of youth brain response (BOLD) to changes in youth problem drinking across proximal (3- and 6-month) and distal (12-month) follow-ups, and (3) the mediational role of BOLD activation on the relationship between therapist behaviors and youth problem drinking outcomes. Measures will be derived from the baseline fMRI scan and behavioral data collected at baseline, 3-, 6- and 12-months.

fMRI preprocessing and single-subject analysis. The first three volumes of each run will be discarded to allow the MR signal to reach steady state. The remaining images in each youth's time series will be motion corrected (Jenkinson, Bannister, Brady, & Smith, 2002) using FSL's MCFLIRT module (FMRIB's Software Library). Images will be spatially smoothed with a 3D Gaussian kernel ($FWHM = 8 \text{ mm}^3$), intensity normalized and temporally filtered with a 50 sec high pass filter FEAT (FMRIB's Easy Analysis Tool) (Smith et al., 2004).

We will utilize a regression approach (GLM - general linear model) to extract regularities with regard to temporal aspects (i.e., time series) of the data. Statistical analysis will be carried out using FILM (FMRIB's Improved Linear Model) with local autocorrelation correction. We will create an explanatory variable (EV) for each trial type (MI-consistent, BAM-consistent, BAM- and MI-inconsistent). For each participant, we will use FILM to obtain a parameter estimate for each EV and create appropriate contrasts. Contrast maps of parameter estimates (PE) for each youth are transformed into a common stereotaxic space using the following 2-step registration prior to the group analyses. Statistical maps will be warped into the common MNI stereotaxic space (Jenkinson et al., 2002) before a random effect group analysis is performed. To do so, (1) the EPI image will be registered to the participant's high resolution T1 weighted image; (2) the T1-weighted high resolution image will be registered to the MNI 152 brain template image; and (3) statistical images

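### The randomised MI-versus-BAM contrast and the 3-month scan have no hypothesis, sample-size step or analysis in the supplied text

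*Combined protocol and SAP*

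**What the plan says.** **Design (Section 6).** Under Experimental Condition, "Half of the enrolled youth will receive 2 60-minute MI sessions". Under Control Condition, "Half of the enrolled youth will be randomized to a control condition to help researchers isolate the mechanisms of MI". The intervention rationale adds that "The unique contributions and ultimate effectiveness of MI cannot be evaluated without a comparison condition". Its example is a finding that "if the youth in the mindfulness condition show greater change in neurocircuitry related to cognitive control" than the MI youth, in a way that tracks behaviour change over follow-up. A second scan is collected: at 3 months "participants will return to OHSU for a final MRI scan identical to the one completed in Session 2". Youth who cannot attend may complete the visit remotely, where "phone/REDCap measures will be offered instead to minimize missing data".

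**Hypotheses (Section 2).** H1 contrasts therapist statement types on BOLD response. H2 relates BOLD to later problem drinking. H3 makes BOLD the mediator between statements and drinking. None names an arm. The cannabis hypotheses 2b and 3b in Section 8 follow the same pattern.

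**Analysis (Section 8).** The list begins "Analyses will be conducted to evaluate (1) the relationship between therapist behavior and youth brain response (BOLD" and continues with the BOLD-drinking relation and mediation. The data source is given as: "Measures will be derived from the baseline fMRI scan and behavioral data collected at baseline, 3-, 6- and 12-months". BAM appears only as one of three trial types in the single-subject model, and under the NILE task description every participant hears all three.

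**Objectives (Section 2).** All 243 youth are described as enrolled in two sessions of MI, with no mention of BAM.

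**The concern.** The protocol randomises youth to a control and says why the control is needed, but the analysis section never uses the allocation. It also collects a second scan from each youth able to attend and gives it no analysis. Followed as written, the plan would report H1 to H3 and leave unanswered the comparison that its own rationale raises. If an arm comparison were then run, its outcome, time point and scan would not have been fixed in the text we have.

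Two related questions are left open. The plan does not say whether H1 to H3 use both arms or MI youth only. The scan called baseline also takes place at the second visit, after Intervention Session 1, so arm could already have affected the BOLD measure used in H2 and H3.

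**Working it through.** **1. The plan's own total.** Section 8 gives N = 204 for H3 and projects 16% attrition. 204 / (1 − 0.16) = 242.9, so 243 reproduces. The 204 comes from a cited mediation source and was taken as stated. The other two figures, 22 for H1 and 68 for H2, are assigned to a statement-type contrast and a BOLD-behaviour association. No step sizes MI versus BAM.

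**2. What an arm comparison could detect** (two-sided 0.05, power 0.80, noncentral t).
- 243 taken before attrition (Section 8): 243 × 0.84 / 2 = 102 per arm, d = 0.39. Normal approximation: 2.80 × √(2/102) = 0.39.
- 243 taken as completers (Section 5a, Number of Subjects): about 121 per arm, d = 0.36.
- Adjusting for baseline multiplies d by √(1 − r²). At 102 per arm, assumed r of 0.3, 0.5 and 0.7 give 0.38, 0.34 and 0.28.

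**3. If H2 and H3 pool the arms and omit arm.** BOLD in H3 is a within-person difference between MI-consistent and MI-inconsistent statements, so a general arm effect on BOLD cancels. Confounding requires arm to shift that difference and also to shift drinking by a route other than BOLD. With shifts s₁ and s₂ in SD units, equal arms and no within-arm link, the induced correlation is (s₁s₂/4) / √((1 + s₁²/4)(1 + s₂²/4)). The documents give no shifts, so these are assumed. Rejection rates are simulated at N = 204 with a nominal 5% test.

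| Shifts (BOLD, drinking) | Induced correlation | Arm omitted | Arm included |
|---|---|---|---|
| 0.2, 0.2 | 0.010 | 5.4% | about 5% |
| 0.3, 0.3 | 0.022 | about 6% | about 5% |
| 0.5, 0.5 | 0.059 | 13% | about 5% |
| 0.5, 0 | 0 | 5.0% | about 5% |

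If arm affects drinking only through BOLD, omitting it does not bias the slope (0.299 against a true 0.30).

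**4. If H1 to H3 use MI youth only.** About 102 completers would face the 204 required for H3. Keeping 204 MI completers would need 2 × 243 = 486 randomised.

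**5. Unplanned looks at the arm contrast.** Assume that the arms do not differ, that any p < 0.05 may be reported, and that correlations between time points and between the two components are 0.3 to 0.7. The chance of at least one such result is 11 to 14% for the index at three time points, and 18 to 27% if binge days and the RAPI are added (nine tests). One named test gives 5%. The eight tests left after naming one still carry 18 to 26%, so they need a label or an adjustment.

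**6. Coding of arm in the A path.** With assumed mean contrasts of 0.6 (MI) and 0.4 (BAM), SD 1 and 102 per arm, 0/1 coding with BAM as reference makes the intercept 0.40 (SE √(1/102) = 0.099), which is the BAM mean. Centred coding gives 0.50 (SE √(1/204) = 0.070), the mean over both arms.

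**7. The 3-month scan.** If 84%, 70% or 60% of youth have both scans (assumed), the detectable arm difference in change is d = 0.39, 0.43 or 0.47 per region at 0.05.

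**The case against.** The strongest reply is that this is a mechanism study. The Control Condition text says that the arm is there to isolate mechanisms, the aims contain no efficacy aim, and H1 to H3 can be tested as stated. All of that stands. A reader might infer that the control was added chiefly to test whether MI reduces drinking more than BAM. The rationale does mention effectiveness, but its worked example is a brain-behaviour link compared between arms, so the documents do not support that as the main purpose.

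A reader might also call any arm result post hoc. That goes too far: the rationale foresees an arm comparison in advance, Section 4 (Study Design) has no text in this copy, and the Supplement behind 2b and 3b is not supplied. What can be said is that the supplied text fixes no outcome, time point, model or alpha for it.

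A third tempting reading is that H2 and H3 pool the arms and are therefore confounded. The plan does not say who is analysed, the documents give no shifts, and the distortion is small at modest ones. Nor does any passage indicate selective reporting; the rates for unplanned looks show what is possible under stated assumptions.

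The reply does not remove the gap. The analysis section is present and silent on arm. Its mention of BAM concerns a stimulus type, and its references to contrasts and to group-level analysis concern trial types and imaging maps.

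**Conclusion.** The point holds as a should-fix. In the supplied text, neither the randomised contrast nor the 3-month scan has a hypothesis, sample-size step or analysis, so an MI-versus-BAM finding would not be prespecified there. H1 to H3 and their sample-size basis are not invalidated by this.

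The lost opportunity is moderate: about d = 0.39 is detectable at 102 per arm, or 0.36 at 121, depending on how the conflict over 243 is resolved. The missing arm term is the lesser matter if the arms are pooled. The unstated analysis set matters more if MI youth only are meant, because the available number would then be half of what H3 requires. The detectable effects follow from the plan's figures; the shifts, correlations and scan-completion rates are assumptions.

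**What to change.** 1. State the analysis set for H1 to H3. If both arms are used, add arm to the H2 models and the H3 B path, and centre it (−0.5/+0.5) wherever it enters the A path.
2. Prespecify MI versus BAM on the plan's own problem-drinking index, adjusted for its baseline value, at one named time point and two-sided 0.05. Declare it secondary, since the aims include no efficacy aim. Label the other time points, binge days and the RAPI exploratory, either with no significance claim or with a multiplicity adjustment. State the detectable effect (about 0.39 with 102 per arm, about 0.36 with 121) and reconcile Section 5a with the attrition paragraph in Section 8.
3. Name a secondary or exploratory between-arm analysis of change in the MFG, IFG and insula contrast from the Session 2 scan to 3 months, and of how that change relates to drinking change. Report the number per arm with both scans.
4. Reconcile the Objectives, where all 243 receive MI, with the two-arm description in Section 6.

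The cost is wording and modest analysis work, with no new data, visits or participants. Each model loses about one degree of freedom; in an assumed case with no arm effect and a slope of 0.20, power is 80.4% with arm against 80.7% without. One declared test is added, and the arm analyses will detect moderate effects only.

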Neuroimaging Session. We conduct the neuroimaging session during the second visit in order to have sufficient time to cater the counselor statements to the participant's in-session change talk statements, and to integrate their thematic content into each youth's individualized fMRI Neural In-Session Language Examination (NILE) task. Session 2 takes place at OHSU's Advanced Imaging Research Center (AIRC). Consistent with the PI's prior work ([name] under review), participants will be required to abstain from alcohol 24 hours prior to the scan as verified before the scan by breathalyzer, and will also complete a urinalysis to corroborate self-report as a measure of drug use and a voluntary test for pregnancy in females. Upon arrival to OHSU, youth will be screened to assure the absence of fMRI contraindications (no metal in body; not pregnant; breath alcohol = 0). Only approved youth will be scanned. We will use the 3T Siemens Prisma that includes 32 RF channels \times 102 coil elements, multi-nuclear support, clinical features (extremity coil, shoulder array coil, spectrus injector), and additional software (e.g., BLADE). fMRI scans will be collected with single-shot full k-space echo-planar imaging (EPI) with ramp sampling correction using the intercommissural line (AC-PC) as a reference (TR: 2.0s, TE: 27ms, α : 70°, matrix size: 64 \times 64, field of view: 24x24, 33 slices, voxel size: 3.75 \times 3.75 \times 4.5 mm). Image-based higher order automatic shimming will be employed. fMRI data will be acquired with the 32-channel phased array-coil. Automated analysis of scanner instability with the Weiskoff method will be carried out using a software tool provided by the MGH. A tilting acquisition will be used to improve the signal dropout and warping in the orbitofrontal cortex (Deichmann et al 2003) similar to our previous published studies ([name] et al 2013b). The subjects will complete a high-resolution structural scan collected for image registration and normalization, followed by the experimental procedure. The

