will be transformed to MNI space using the transformations matrices from step 2. Coordinates will be reported in MNI space. All registration will use FNIRT (FMRIB's Nonlinear Image Registration Tool).

To test **Hypothesis 1**, that MI-consistent therapist behaviors will be associated with greater BOLD response (MFG, IFG, insula) than MI-inconsistent therapist behaviors, we will utilize the same procedure used in our pilot study ([name] et al under review-a). Group-level activations will be evaluated for MI-consistent vs. MI-inconsistent for change talk (CT) and sustain talk (ST) separately across the whole brain and thresholded using a false discovery rate (FDR) set to a false-positive $p < 0.05$. Following our prior work ([name] et al under review-a, [name] et al 2013b), to test **Hypothesis 2a** (from original submission), that BOLD response will be directly associated with proximal (3-, 6-month) and distal (12-month) behavior change (reductions in youth problem drinking), we will utilize an index of youth problem drinking (past month binge drinking days; derived from TLFB + past month alcohol-related problems; derived from RAPI). We will conduct linear regression analyses in FSL with baseline measures of alcohol use behavior and alcohol problems included as regressors to assess correlations between BOLD response and behavior change for youth problem drinking at each follow-up time point. To test **Hypothesis 2b** of the Supplement, that greater BOLD response will be directly associated with proximal (3-, 6-month) and distal (12-month) behavior change (reductions in youth cannabis use), we will utilize an index of youth problem cannabis use (past month cannabis use days; derived from TLFB + past month cannabis related problems; derived from Cannabis Problems Questionnaire). We will conduct linear regression analyses in FSL with baseline measures of cannabis use behavior and cannabis problems included as regressors to assess correlations between BOLD response and behavior change for youth problem cannabis use at each follow-up time point.

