To test **Hypothesis 3a** (from original submission) and 3 b (from supplement) that BOLD response (MFG, IFG, insula) will mediate the relationship between therapist behaviors (MI-consistent) and proximal and distal reductions in youth problem substance use (drinking; cannabis use), we will use the product of coefficients method (Sobel 1982). Because the distribution of the product of coefficients is typically not normal, we will apply appropriate asymptotic confidence limits (MacKinnon et al 2007) following Co-I [name]'s prior work examining causal chains in MI (Moyers et al 2009). Coefficients and standard errors for the A and B paths will be computed in FSL using the variables from Hypotheses 1 and 2 (i.e. signal change difference between MI-consistent and MI-inconsistent language, with (a) past month binge drinking/alcohol-related problems at 3-, 6- and 12-months; (b) past month cannabis use/cannabis-related problems at 3-, 6- and 12- months), and tested using the PRODCLIN macro (MacKinnon et al 2007). We will perform separate tests for proximal and distal drinking, each tested at $\alpha = .05$.

9) Privacy, Confidentiality and Data Security

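### The Hypothesis 2 and 3 models contain no randomized-arm term, so a BOLD–drinking slope pooled over MI and BAM is open to confounding by arm

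*Combined protocol and SAP*

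**What the plan says.** Section 6 (Intervention Session 1 and Intervention Overview) gives half of the enrolled youth two MI sessions and half two BAM sessions, by randomization. The Control Condition paragraph says BAM is there to single out how MI works. The rationale for the intervention approach adds that MI's own contribution cannot be judged without a comparison.

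Section 8 (Analysis Plan) then sets out the tests:

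- Hypothesis 2a: "linear regression analyses in FSL with baseline measures of alcohol use behavior and alcohol problems included as regressors".
- Hypothesis 2b: "linear regression analyses in FSL with baseline measures of cannabis use behavior and cannabis problems included as regressors".
- Hypotheses 3a and 3b: "Coefficients and standard errors for the A and B paths will be computed in FSL using the variables from Hypotheses 1 and 2", where the BOLD variable is the "signal change difference between MI-consistent and MI-inconsistent language".

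None of these mentions randomized arm, a BOLD-by-arm term, separate models by arm or a restriction to MI youth, and no other section supplies one. BAM enters section 8 only as a type of statement: "We will create an explanatory variable (EV) for each trial type (MI-consistent, BAM-consistent, BAM- and MI-inconsistent". Every participant hears all three types, so this is not the randomized arm.

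On timing, section 8 states: "Measures will be derived from the baseline fMRI scan". Section 6 (Neuroimaging Session) places that scan after treatment has begun: "We conduct the neuroimaging session during the second visit". The task is built from the youth's MI or BAM session of the week before.

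Section 2 (Objectives) still describes all 243 youth as receiving MI.

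**The concern.** Hypotheses 2 and 3 relate one post-randomization variable (BOLD at the second visit) to another (drinking or cannabis use at 3, 6 and 12 months). Randomization does not protect that relation. If one arm has both a larger BOLD contrast and a larger fall in drinking, pooling the arms produces a BOLD–drinking correlation even when none exists inside either arm. Shifts that run against a true link can hide it. In Hypothesis 3 the affected coefficient is the B path, so the error carries into the indirect effect.

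Adjusting for baseline drinking does not help. Randomization balances baseline drinking between arms, so it carries no information about an arm effect that arises afterwards.

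There is also a question of interpretation. A slope pooled over arms cannot show whether the link depends on having received MI, and that is the use for which the protocol says the control was added.

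**Working it through.** **The plan's own figures.** Section 8 (Power Analysis) needs 204 completers for Hypothesis 3. Under The Impact of Attrition it says "we project losing 16% of the proposed sample". 204/0.84 = 242.9, so 243, as stated. With half in each arm, 243 × 0.84/2 = 102 completers per arm. The Hypothesis 2 effect of d = 0.70 reproduces the stated 68 as a two-group t-test (two-sided .05, power .80). As a correlation it is r = 0.70/√(0.70² + 4) = .33.

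**False positives from leaving arm out.** Assumptions: equal arms; BOLD contrast and baseline-adjusted outcome each with SD 1 within arm; true within-arm slope zero; arm shifts BOLD by dB and outcome by dY. The documents give neither shift. The correlation induced by pooling is

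ρ = (dB·dY/4) / √[(1 + dB²/4)(1 + dY²/4)].

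A two-sided .05 test on N = 204 rejects with probability P(Z > 1.96 − δ) + P(Z < −1.96 − δ), where δ = atanh(ρ)·√201.

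Example for 0.5/0.5: ρ = 0.0625/1.0625 = .0588; δ = 0.0589 × 14.18 = 0.835; rejection = .130 + .003 = .133.

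| Assumed shift, BOLD/outcome (SD) | Induced ρ | Pooled, formula | Pooled, simulated | Arm in model, simulated |
|---|---|---|---|---|
| 0.2/0.2 | .010 | 5.2% | – | – |
| 0.3/0.3 | .022 | 6.1% | 6.1% | 5.1% |
| 0.5/0.3 | .036 | 8.0% | 8.2% | 5.1% |
| 0.5/0.5 | .059 | 13.3% | 13.7% | 5.1% |
| 0.8/0.5 | .090 | 24.9% | 25.1% | 4.9% |

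The simulations used ordinary least squares with 40,000 runs. Since ρ depends on the product dB·dY, a zero shift on either variable gives ρ = 0 and a 5% rate; 0.8/0 gives 5.0%.

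**Power of a BOLD-by-arm test.** Comparing two independent correlations at 102 per arm, the standard error on the Fisher z scale is √(1/99 + 1/99) = 0.142. Power is found from [atanh(r_MI) − atanh(r_BAM)]/0.142 against 1.96. The upper r is the plan's own d = 0.70; the lower (.195) is an assumption.

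| Assumed r in MI | BAM slope 0 | BAM 25% of MI | BAM 50% of MI |
|---|---|---|---|
| .195 | .28 | .18 | .11 |
| .33 | .67 | .45 | .24 |

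The test stays below .80 throughout this range.

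**The case against.** The strongest reply is that Hypotheses 1 to 3 are not worded by arm, so a pooled slope answers Hypothesis 2 as written. That stands: the protocol promises no arm contrast, and the BOLD-by-arm test is an addition, which is why it is proposed only as exploratory. It does not remove the bias that a pooled slope can carry.

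A second reply is that the arms may differ little. Both are active, of equal length, open with the youth's drinking story and review drinking at the second session. The within-person contrast also removes general response to counselor statements. This stands as a limit on size, and it makes the upper rows of the first table less likely. It does not exclude an arm difference in the contrast itself, since only MI youth have just had an MI session.

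Third, pooling is inferred. The plan does not say which youth enter these models, and an analysis of MI youth alone would have no confounding by arm. That also stands; the remedy is to state the analysis set.

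Some stronger readings are tempting but not supported:

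- A reader might infer that the protocol expects the arms to differ on both BOLD and drinking. The rationale section offers only a hypothetical example about change in cognitive-control circuitry, not a prediction about this contrast.
- A reader might call 243 too small because it makes no allowance for two arms. For hypotheses that are not arm-specific, that is no error.
- A reader might count the BAM-consistent regressor as an unused analysis. Those trials have to be modelled whether or not a hypothesis uses them.

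**Conclusion.** The omission is certain from the text; the harm is conditional. A pooled slope is confounded only if arm shifts both the BOLD contrast and the outcome. With zero within-arm slope at N = 204, a single pooled test then rejects about 5% to 25% of the time over assumed shifts of 0.2/0.2 to 0.8/0.5 SD, against 5% with arm included. These rates are for one uncorrected test, and the shifts are assumptions. The only image-level threshold the plan states is the false discovery rate for Hypothesis 1.

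The documents do not support saying that the planned slope is biased, only that it is open to bias which one extra term would remove. Nor do they support saying that the plan fails to test its stated hypotheses. It does lack any specified analysis that puts the control arm to its declared use. The change is worth making because it protects the estimate at almost no cost.

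**What to change.** 1. State in section 8 that Hypotheses 2 and 3 use both arms.
2. Add randomized arm as a regressor in the H2a and H2b models and in the B path of H3a and H3b.
3. As an exploratory analysis, enter one outcome regressor per arm in the FSL group design, with contrasts for each slope and for their difference. Base any claim that the link is specific to MI on that difference. State its power as a range (about .11 to .67 at 102 per arm under the assumptions above), and say that a null result does not show equal slopes.
4. Correct section 2 so that it describes the two-arm design.

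The arm term costs one degree of freedom and the slope difference one more. No new data, visits or participants are needed. The exploratory step adds tests: two substances by three follow-ups gives six slope differences for each region examined, and the plan should label them all exploratory.
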